Inclusion Criteria: Subjects with CF (medical record evidence of cystic fibrosis transmembrane conductance regulator mutation or sweat chloride test or nasal voltage difference, **and** 1 or more clinical findings of CF), age 12 or greater with an FEV₁ >30% predicted (within the last 14 days) and oxygen saturation \geq 90% on FiO₂ \leq 50%, admitted for an exacerbation, able to provide written informed consent or assent.

Exclusion Criteria: Pregnancy, hemoptysis more than 60 mL within the last 30 days, use of any investigational study drug within the last 30 days, initiation of hypertonic saline within the last 30 days, known intolerance to hypertonic saline, serum creatinine 2 mg/dl or more, active malignancy in the last year, on waiting list for lung transplantation, received a solid organ transplant, lack of FEV₁ data from the last 14 days and previous participation in this study.

Experimental Treatment: Aerosolized 15% xylitol, 5 ml twice a day for 2 weeks using Pari LC nebulizer with Vios compressor, (Pari Inc, Monterey, CA) . Xylitol crystals are

made as food additives by Danisco Cultor, USA. Aerosol solution is sterile, non-pyrogenic, preservative-free solution for inhalation made by UI Pharmaceuticals (Iowa City, IA).

Control Treatment: Hypertonic 7% saline (UIHC pharmacy) 4 ml twice a day for 2 weeks using the same kind of nebulizer.

Screening and Baseline Visit: On the day of admission for exacerbation, informed consent obtained in subjects whose admission spirometry (or spirometry within the last 14 days prior to admit date) shows an FEV₁ >30% predicted. Once consented, subjects will be randomized to either xylitol or saline group as per the randomization code previously generated by the statistician. Demographics, current medications use and the revised CF quality of life questionnaire (CFQ-R) will be completed. Spontaneously expectorated sputum will be collected and processed for cell count and cytokines and quantitative cultures. Blood will be collected for chemistry and liver function tests (LFT). Pregnancy test will be done in women. All medication use during hospitalization will be recorded. Treatment will begin the day after admission for an exacerbation. Results from spirometry that is routinely done twice a week for inpatients will be recorded. All spirometry testing will follow the 2005 American Thoracic Society guidelines.

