First dose pre and post spirometry: All subjects will undergo spirometry before and 20 minutes after the first study drug dose as follows.

Perform baseline spirometry and measure SpO₂. Multiply the patient's best FEV₁ by 0.80 to obtain 20% fall in FEV₁ value.

Premedicate subject with 4 puffs albuterol and wait 15-30 min.

Begin study drug nebulization.

Wait for 15-30 minutes and repeat spirometry and SpO₂.

Subject is excluded from the study if SpO₂ is <89% or FEV₁ declines by 20% or greater from baseline.

Administration: Subjects will take their routine inhaled medicines followed by chest physical therapy. All subjects will then receive 2-4 puffs of albuterol metered dose inhaler 15-30 minutes before the study drug. Finally the study drug will be inhaled. All empty, unused and partially used study drug containers will be tracked by the investigators. Subjects will be required not to use any new treatments if not medically indicated during the study period.

Day 14 follow-up: Subjects will undergo spirometry and sputum collection and answer CFQ-R questionnaire. Blood draw for LFTS and electrolytes will be done if not done for clinical reasons. If subjects are discharged prior to 14 days of xylitol use, nebulizer solutions will be sent home. They will be asked to keep a log of nebulizer use and bring back empty and unused vials on follow-up visit (Day 10-15, preferably day 14). They will undergo spirometry and sputum collection and questionnaire administration on that day. If subjects don't return on this day, they will have a phone follow-up for adverse events and compliance.

Phone follow-up: Week 1, Day 90 and Day 180 after discharge: Subjects will be contacted by phone at these time points to enquire about further pulmonary exacerbations, admissions, and other AEs.

In the event of bronchospasm: Subjects will alert the nurses or study team members. Nebulized bronchodilators will be immediately administered. Once symptoms resolve, they will undergo spirometry using a portable handheld spirometer by a trained user. If the subjects dropped FEV₁ by 20% or greater from their baseline, they will not receive further study drug. However, they will remain in the study for completion of data collection.

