The primary outcome is FEV₁ change from baseline. To test for a difference in the mean change between the treatment group and the control group, a two-sample t-test will be conducted. To estimate the difference in the mean change, the equivalent confidence interval procedure will be used. Prior to conducting the test, normality will be assessed for each group based on normal probability plots. If gross departures from normality are observed, a Wilcoxon rank sum test will be performed instead of the t-test. (With group sample sizes of 30, the t-test is fairly robust to departures from normality.)

The same analytical approach will be used to assess differences in the group means for the following variables: the primary outcome of change in respiratory symptom score, and the efficacy outcomes of change in density of colonization (per gram of sputum),

change in sputum cytokines and cell counts, and responses to all Likert-scale questions on the CFQ-R.

To analyze group differences in the efficacy outcome of time to next exacerbation, a time-to-event analysis will be conducted. Kaplan-Meier estimates will be obtained for each survival curve (where failure is defined by exacerbation). To compare the survival distributions, a log rank test will be employed.

To compare the proportion of subjects in each group who have experienced any adverse events, Fisher's exact test will be used. Since certain subjects may experience multiple adverse events, we will also compare the incidence of adverse events in each group. For this comparison, a test will be conducted to contrast the mean number of events in each group, where the two samples of event counts are treated as arising from independent Poisson distributions. To estimate the difference in group proportions and the difference in group means, equivalent confidence interval procedures will be employed.

The preceding inferential procedures will be conducted for individual types of adverse events (e.g., cough, chest tightness, headache), as well as the aggregate of all adverse events. Fisher's exact test will also be used to compare the compliance proportion and the proportion of rescue bronchodilator use in each group.

Since this study is a randomized, controlled clinical trial, we expect the treatment group and the control group to be balanced with respect to factors that could affect the primary

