and efficacy outcomes, such as age and gender. For such variables, descriptive statistics will be compiled for each group to ensure that the randomization has been effective. If a marked difference is observed in the distribution of any variables, an analytical approach will be utilized that will allow us to control for these variables. Specifically, the t-test can be replaced with an analysis of covariance model, the log-rank test can be replaced with a Cox proportional hazards model, Fisher's exact test can be replaced with a logistic regression model, and the two-sample Poisson test can be replaced with a Poisson regression model.

All analyses will be performed by the study statistician using SAS version 9.2 (SAS Institute, NC).

Risks: Exposure to xylitol and hypertonic saline is expected to not elicit any significant symptoms other than some cough; however we recognize that there may be a possibility of bronchospasm with the hyperosmolar xylitol in a subgroup of subjects with CF who have bronchial hyperresponsiveness that was not known previously.

Blood draw and spirometry are a part of standard care and will not pose added risks.

With the admission labs that are routinely done, we will collect another red top tube for liver function tests if they were not planned. Answering questions may involve some concentration and may be boring.

Risks are minimized as follows: In the event of bronchospasm with the study drug, immediate treatment with bronchodilators is available. The subject will undergo a spirometry and if the FEV₁ has declined by 20%, the subject will be terminated from the

study. Blood draw will be performed by trained nurses or the hospital IV team with minimal discomfort. Spirometry will be done by experienced respiratory therapists. Symptom questionnaire will be administered by well-trained interviewers and will be as brief as possible.

Confidentiality: All the test results and questionnaire will be stored in the research office under lock and key with access only to the investigators. Once all testing is complete and data is entered for analysis, there will be no identifiers connecting the subject to the data. All results will be reported in summary without identifying the subjects. Blood and urine specimens will not be stored for future use.

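### The continuous outcomes are compared without adjustment for their own baseline; pre-specified ANCOVA, on the log scale for skewed sputum outcomes, would usually be more precise and costs about 1% of interval width at worst

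*Combined protocol and SAP*

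**What the plan says.** Under Outcomes, the primary analysis of FEV1 change reads: "To test for a difference in the mean change between the treatment group and the control group, a two-sample t-test will be conducted", with a matching confidence interval. The fallback is: "If gross departures from normality are observed, a Wilcoxon rank sum test will be performed instead of the t-test". The same approach is extended to change in respiratory symptom score and colonization density, and to "change in sputum cytokines and cell counts, and responses to all Likert-scale questions on the CFQ-R". No covariate appears in any of these comparisons, and the analysis text names no transformation. The log scale appears only in the sample-size paragraph for log CFU.

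Adjustment comes in at the end of the section and is conditional: "If a marked difference is observed in the distribution of any variables", the plan will control for those variables. The method is worded as a possibility: "Specifically, the t-test can be replaced with an analysis of covariance model". No threshold is given. Age and gender are the examples, and the baseline value of the outcome is not mentioned.

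The baselines are collected. For FEV1, under First dose pre and post spirometry: "All subjects will undergo spirometry before and 20 minutes after the first study drug dose as follows". The Screening and Baseline Visit collects sputum for culture, cytokines and cell count, and the CFQ-R. Follow-up is stated as: "Day 14 follow-up: Subjects will undergo spirometry and sputum collection and answer CFQ-R questionnaire". Inpatient spirometry is also kept: "Results from spirometry that is routinely done twice a week for inpatients will be recorded".

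**The concern.** A change score implicitly fixes the slope of follow-up on baseline at 1. Unless the true slope is close to 1, estimating it leaves less residual variance and a narrower interval. Here the baselines are in hand, about 30 subjects per group are planned, and a confidence interval is to accompany each comparison, so precision is the main thing the analysis method can still improve.

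Tying ANCOVA to an observed imbalance does not recover this. The precision comes from the correlation between baseline and follow-up, which is present whether or not the groups differ by chance at baseline. The conditional rule also leaves the main model to be chosen after the data are seen.

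For sputum cytokines and cell counts, which are often strongly right-skewed, no scale is fixed. The only remedy offered is a Wilcoxon test on the raw values.

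A related gap is that neither Endpoints nor Outcomes says which follow-up test or unit defines FEV1 change, although pre-dose, post-dose, twice-weekly and Day 14 spirometry are all recorded.

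**Working it through.** **Inputs from the documents.** 30 per group, two-sided 0.05; log CFU SD 1.5, effect 1.5, 80% power, 17 per group (Statistical analysis and Outcomes). **Not given, so assumed over a range:** the baseline-to-Day-14 correlation ρ, and k = Day 14 SD / baseline SD.

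**1. The plan's own figure.** A two-sample t-test with SD 1.5 and difference 1.5 (noncentral t) has power 78.1% at 16 per group and 80.7% at 17. The stated 17 reproduces.

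That SD describes a level, whereas the planned analysis is of change. The SD of change is 1.5·√(2(1−ρ)) at k = 1:

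| ρ | 0 | 0.3 | 0.5 | 0.7 |
|---|---|---|---|---|
| SD of change | 2.12 | 1.77 | 1.50 | 1.16 |
| n per group, 80% power | 33 | 23 | 17 | 11 |
| Power at 30 per group | 77% | 90% | 97% | >99% |

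So 17 is right for a change score only near ρ = 0.5. Thirty per group stays adequate unless ρ is below about 0.08 or many sputum samples are missing. This is a clarification and alters no decision.

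**2. Interval width, ANCOVA against change score.** In units of the baseline variance, the change score has variance 1 + k² − 2ρk and the ANCOVA residual has variance k²(1 − ρ²). Hence

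CI ratio = √[k²(1 − ρ²) / (1 + k² − 2ρk)] × cost.

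The cost of estimating one slope, with N = 2n analysed, is √(1 + 1/(N − 4)) times the ratio of t critical values on N − 3 and N − 2 df. At N = 60 this is √(1 + 1/56) × 1.0004 = 1.009.

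Example, k = 1 and ρ = 0.5: √(0.75/1.00) × 1.009 = 0.866 × 1.009 = 0.874.

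| k | ρ 0.3 | 0.5 | 0.7 | 0.8 | 0.9 | 0.95 |
|---|---|---|---|---|---|---|
| 0.9 | 0.77 | 0.82 | 0.87 | 0.90 | 0.91 | 0.90 |
| 1.0 | 0.81 | 0.87 | 0.93 | 0.96 | 0.98 | 1.00 |
| 1.1 | 0.85 | 0.91 | 0.97 | 0.99 | 1.01 | 1.00 |
| 1.2 | 0.88 | 0.94 | 0.99 | 1.01 | 1.00 | 0.95 |

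The ratio exceeds 1 above ρ of about 0.96 at k = 1, and for ρ of about 0.83 to 0.95 at k = 1.1. It can never exceed the cost term, which is reached when the true slope is 1: 0.9% at 30 per group, 1.1% at 25, 1.5% at 20 and 1.8% at 17. Simulated type I error is 4.9% to 5.2% for both methods.

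**3. The conditional rule.** The trigger is undefined. As an illustration, read it as p < 0.05 on the outcome's own baseline. It then fires in 5% of trials, and the mean CI narrows by only 0.7% at ρ = 0.3 and 0.4% at ρ = 0.5, against 19% and 13% when ANCOVA is always used.

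**4. Skewed sputum outcomes.** Simulated power, assuming lognormal data, 30 per group and a shift of two-thirds of a log-SD; where three values are given they are for log-SD 1/1.5/2:

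| Analysis | ρ = 0.7 | ρ = 0.5 |
|---|---|---|
| t-test, raw change | 0.48/0.26/0.14 | – |
| ANCOVA, raw | 0.73/0.51/0.33 | – |
| Wilcoxon, raw change | 0.69/0.63/0.59 | 0.50/0.46/0.43 |
| t-test, log change (noncentral t) | 0.91 | 0.72 |
| Rank ANCOVA | 0.91 | 0.80 |
| Log ANCOVA | 0.94 | 0.83 |

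**5. CFQ-R items.** Assuming a 4-point item with evenly used categories, latent ρ 0.5 and a shift of 0.6 SD, power is 0.64 with ANCOVA, 0.50 for a t-test on change and 0.56 for a t-test on the Day 14 response alone.

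**The case against.** The strongest reply is that the primary outcome may gain little. No FEV1 SD or correlation is given. If FEV1 repeats closely over two weeks (ρ of 0.8 or more), the table shows between about a 4% gain and a 1% loss when the Day 14 SD is equal or moderately larger. The larger gains need correlations that the documents do not support for FEV1. The trial is described as a pilot safety study powered on adverse events, with no FEV1 margin and no decision rule tied to interval width. This stands: the FEV1 gain is undocumented and may be nil.

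Second, for grossly skewed data the plan already moves to Wilcoxon, so the raw t-test powers are not the fair comparator, and most of the remaining gain comes from the log scale. This also stands. At ρ = 0.7 a t-test on log change reaches 0.91 against 0.94 for log ANCOVA. At ρ = 0.5 the gap is wider, 0.72 against 0.83. Colonization density may already be intended as log CFU, in which case the scale point applies mainly to cytokines and cell counts.

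Third, the conditional clause covers any variable and could include a baseline outcome value. It could, but it is optional, has no threshold and does not provide routine adjustment.

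Fourth, 1% is not the worst case where sputum is missing. True, but the cost is still only 1.8% with 17 per group analysed.

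**Conclusion.** The concern holds as a matter of efficiency. The planned t-tests are valid under randomisation, and nothing here suggests bias. Pre-specified adjustment for the outcome's own baseline is the better main analysis because the trade is lopsided: at most about 1% wider intervals at 30 per group, against 2% to 19% narrower ones for correlations from 0.9 down to 0.3 with equal SDs. The benefit is likely to be larger for outcomes that correlate less with their baseline, and smallest, possibly absent, for FEV1. For skewed sputum outcomes, fixing the log scale brings most of the gain and adjustment adds to it. All gains rest on assumed correlations, SD ratios and, for sputum and CFQ-R, assumed distributions; the worst-case cost depends only on the number analysed. The change should be made.

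**What to change.** In Outcomes, name ANCOVA (treatment plus the baseline value of the same variable) as the main analysis of each continuous outcome that has a baseline:

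- **FEV1:** baseline from the spirometry before the first dose; Day 14 value as the outcome, if that is the intended time point; state litres or % predicted.
- **Colonization density, cytokines, cell counts:** log scale with a stated rule for zero or below-detection values; rank-based ANCOVA if still grossly skewed. Report ratios of geometric means with 95% CI.
- **CFQ-R:** adjust each item for the baseline response to that item.
- **Symptom score:** the same, if it is measured at baseline; the baseline visit does not list it.

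Report adjusted differences with 95% CI for outcomes that are not logged. Keep the unadjusted t-test and the Wilcoxon test as sensitivity analyses. Make imbalance-triggered adjustment a sensitivity analysis with covariates named in advance; the Cox, logistic and Poisson alternatives can stay on that footing. In the log CFU paragraph, state the assumed correlation, or base the check on ANCOVA, which needs at most about 18 per group if 1.5 is also the Day 14 SD.

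The cost is SAP wording and one degree of freedom per model. No new data are needed and the planned 30 per group is unchanged.

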However, if a subject consents to future use and some of their specimens have already been used for research purposes, the information from that research may still be used.

Statistical analysis: We plan to enroll a total of 60 subjects for this study. These subjects will be randomly assigned to the treatment (xylitol) and control (saline) groups, with a goal of 30 subjects in each group. Since this is a pilot safety study, it has been primarily powered to detect common adverse events. Assuming that the likelihood of a subject experiencing an adverse event is no less than 5%, a sample size of 30 subjects ensures 80% power towards event detection [16]. (In other words, with a group sample size of 30, the probability of observing at least one adverse event in the group is at least 80%.)

Study Performance

Accrual will be assessed on a monthly basis. We will examine the number of screened subjects, those meeting eligibility criteria, the number of persons consenting to participate and the number of randomized. The rate of accrual will be tracked versus the expected number to achieve the target of 60 participants randomized.

We will also track the completion number and proportion by time. The number of study terminations and reason for termination will be measured. The subject will undergo a spirometry and if the FEV₁ has declined by 20%, the subject will be terminated from the study.

Baseline

The composition of the study sample will be described in aggregate. Comparison of randomized participants of baseline characteristics will be analyzed using 2 sample t-test,

Wilcoxon rank sum test, and analysis of variance (ANOVA) as indicated by the type and characteristics of the variable.

Outcomes

To assess the adequacy of these group sample sizes for testing a trend in efficacy, we consider the outcome of log CFU. We assume an average density of colonization of 6.5 log CFU with a SD of 1.5 log CFU among CF subjects. To detect a reduction of 1.5 log CFU in the xylitol group with 80% power, the required sample size is 17 subjects per group. (This computation is based on a two-sided, two-sample t-test conducted at the 0.05 level of significance.) Data from all patients who have received at least one dose of the drug or placebo will be analyzed. Thus, the analysis will be based on intention to treat. All tests will be two-sided, and conducted using a significance level of 0.05.

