Stopping criteria: If any subject drops his/her FEV₁ % predicted by 20%, we will stop further exposures. If 3 subjects drop their FEV₁ by 20% the treatment assignment will be unblinded and they were all in the xylitol group, the study will be closed for further recruitment.

Safety Monitoring: Any unexpected fatal or life-threatening adverse event will be reported to the Food and Drug Administration (FDA) by phone, fax or email no later than 7 days of occurrence. Any other serious and unexpected adverse event associated with the use of xylitol will be reported to the FDA within 15 days of occurrence. Please see DSMP for a detailed safety plan.

REFERENCES

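### FEV₁ is measured before and after the first dose in every subject, but no between-arm analysis of that change or of 20% falls is specified, and a later comparison may lose the affected subjects

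*Combined protocol and SAP*

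**What the plan says.** The section on first-dose spirometry states: "All subjects will undergo spirometry before and 20 minutes after the first study drug dose as follows". The steps that follow put albuterol between the baseline reading and the study drug, and repeat spirometry 15 to 30 minutes after nebulization. The use given there for the result is a gate: "Subject is excluded from the study if SpO₂ is <89% or FEV₁ declines by 20% or greater from baseline".

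The Risks section recognises "a possibility of bronchospasm with the hyperosmolar xylitol in a subgroup of subjects with CF".

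Under Outcomes the primary variable is FEV₁ change from baseline. For it, "To test for a difference in the mean change between the treatment group and the control group, a two-sample t-test will be conducted", with a Wilcoxon rank sum test instead if normality clearly fails. Neither Endpoints nor Outcomes says at which visit the change is taken. On the analysis set, Outcomes says: "Data from all patients who have received at least one dose of the drug or placebo will be analyzed".

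A subject whose FEV₁ falls by 20% meets different rules in different places:

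- First-dose section: excluded from the study.
- Study Performance, repeated in the text on minimizing risks: "The subject will undergo a spirometry and if the FEV₁ has declined by 20%, the subject will be terminated from the study".
- Bronchospasm paragraph: study drug stops, and "However, they will remain in the study for completion of data collection".
- Stopping criteria: "If 3 subjects drop their FEV₁ by 20% the treatment assignment will be unblinded", and recruitment closes if all three were on xylitol.

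**The concern.** The first-dose pair is the only FEV₁ measurement scheduled around a dose in every subject, so it bears most directly on the named risk. The plan gives it no between-arm analysis.

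If subjects with a large first-dose fall then leave and supply no later FEV₁, a comparison at a later visit contains only those who tolerated the first dose. The loss would be selective: the more subjects xylitol affects acutely, the more drop out of the xylitol mean. A later value also carries recovery from the exacerbation that led to admission, which adds variation unrelated to acute tolerance. In a trial whose purpose is safety, the primary comparison could look reassuring because the harmed subjects are absent from it.

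**Working it through.** **1. The plan's own figures.** At least one event among 30 at a 5% rate: 1 − 0.95³⁰ = 0.785, close to the stated 80% (n = 32 gives 0.806). For log CFU (difference 1.5, SD 1.5), the two-sample t-test at 17 per group has power 0.807, so 17 is confirmed. Neither calculation concerns FEV₁. The documents give no FEV₁ SD and no expected rate of 20% falls, so every FEV₁ input below is an assumption.

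**2. What 30 per arm can detect in mean FEV₁ change.** At two-sided 0.05 and 80% power the detectable difference is 0.736 SD. For assumed SDs of 5, 10 and 15 points this is 3.7, 7.4 and 11.0 points.

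**3. Size of the possible bias.** Let k of 30 xylitol subjects have a mean change of −25 points and the other 30 − k a mean change of m. With all 30 counted, and the fall taken as the affected subject's outcome, the mean is [(30 − k)m − 25k]/30. With the k subjects left out it is m. The shift is (k/30)(25 + m).

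| k | m = 0 | m = 5 | m = 10 |
|---|---|---|---|
| 3 | 2.5 | 3.0 | 3.5 |
| 5 | 4.2 | 5.0 | 5.8 |

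These shifts are of the same order as the lower part of the detectable range in step 2.

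**4. Is the closure rule a substitute?** Three falls on xylitol and none on saline, with 30 per arm, give Fisher p = 0.24. Five against none gives 0.052 and six against none 0.024. The rule is a trigger and estimates nothing.

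**5. What a first-dose comparison would add.** Simulation with 20,000 runs and 30 per arm: control changes are normal with mean 0; a fraction q of xylitol subjects have a further 30-point fall.

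| q | Test | SD 6 | SD 8 | SD 10 |
|---|---|---|---|---|
| 15% | t-test | 40% | 32% | 26% |
| 15% | Wilcoxon | 16% | 16% | 15% |
| 20% | t-test | 60% | 49% | 40% |
| 20% | Wilcoxon | 26% | 26% | 25% |

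The Wilcoxon rows matter because a cluster of large falls could trigger the plan's own switch to that test. Power is modest throughout.

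**6. Precision of the proportion with a 20% fall.** Exact (Clopper-Pearson) 95% limits: 0 of 30 gives an upper limit of 1 − 0.025^(1/30) = 11.6%; 3 of 30 gives 2.1% to 26.5%. The plan calls for neither interval.

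**The case against.** A reader might infer three stronger things, none of which the documents support.

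- *That the first-dose reading serves only to exclude.* A 20% fall also counts towards the closure rule, and Study Performance tracks terminations with their reasons.
- *That acute bronchospasm is never compared between arms.* The adverse-event definition takes in any abnormal symptom or sign temporally associated with study drug, so bronchospasm qualifies. Events are compared by Fisher and Poisson tests, by type and in aggregate, with confidence intervals, and the listed types are only examples. Rescue bronchodilator use has its own Fisher test.
- *That affected subjects leave the primary analysis.* The stated analysis set is everyone dosed, and the bronchospasm paragraph keeps subjects with a 20% fall in data collection. Nor is Day 14 named as the primary time point: inpatient spirometry is also recorded twice weekly, and a first-dose reading of the outcome is not ruled out.

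The closure rule also limits how far harm could run unnoticed. If 15% or 20% of xylitol subjects fall by 20%, the chance of at least three among 30 is 85% or 96%. With no falls on saline, that would close recruitment.

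All of this stands, and it narrows the point. It does not remove it. No FEV₁ threshold defines an adverse event, so a fall without symptoms may go uncounted. Rescue use is a proxy. Withdrawal is listed as a safety assessment, but no between-arm test is named for it. The protocol concedes that blinding is not assured, so an objective measure is worth more than reported symptoms. A promise to analyse all dosed subjects does not supply a later FEV₁ for someone who has been excluded.

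**Conclusion.** The point holds as an omission with a possible bias, which the documents do not show to be certain. No between-arm analysis of first-dose FEV₁ change or of 20% falls is specified, the primary change has no time point, and the disposition rules conflict with no provision for missing FEV₁. If subjects with a fall do supply no later value, the xylitol mean could be flattered by 2.5 to 5.8 points. That figure assumes 3 to 5 of 30 affected, a mean fall of 25 points, and a mean change of 0 to +10 points in the rest. If they remain for data collection, the bias shrinks or disappears, but the acute response is still not analysed.

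The benefit of the added analyses is mainly an estimate with an interval: on the assumed rates and SDs, power is 26–60% with the t-test and 15–26% with Wilcoxon. That suits a pilot safety study. The change should be made, but the gap does not invalidate the design.

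**What to change.** In Outcomes:

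1. State the time point of the primary FEV₁ comparison.
2. Add the percent change in FEV₁ from before to after the first dose, compared between arms as a mean difference with 95% CI, in all dosed subjects including those then excluded. Albuterol precedes the dose in both arms, so the between-arm difference is the quantity to interpret, not the change within one arm.
3. Report the number and proportion per arm with a fall of 20% or more, at the first dose and at any time, with exact 95% CIs and the between-arm difference. State the scale of the fall: the first-dose section uses a relative fall (best FEV₁ × 0.80), while Stopping criteria refers to percent predicted.
4. Say how FEV₁ is handled when later values are missing after exclusion or stopping of study drug.

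Separately, the sponsor should reconcile the disposition statements in the first-dose section, the bronchospasm paragraph, Study Performance and the text on minimizing risks. Which rule applies is for the sponsor to decide; the analysis then has to follow it.

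The cost is a few sentences in the plan, two more tables and one added secondary safety comparison. No new measurement and no larger sample is needed.
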